9.5. Interim Analyses

The interim analyses were performed prior to Amendment 6.

9.6. Data Monitoring Committee or Other Independent Oversight Committee

The EDMC was retired after study futility conclusions prior to Amendment 6.

10. SUPPORTING DOCUMENTATION AND OPERATIONAL CONSIDERATIONS

10.1. Appendix 1: Regulatory, Ethical, and Study Oversight Considerations

10.1.1. Regulatory and Ethical Considerations

This study will be conducted in accordance with the protocol and with the following:

- Consensus ethical principles derived from international guidelines including the Declaration of Helsinki and CIOMS International Ethical Guidelines;
- Applicable ICH GCP guidelines;
- Applicable laws and regulations, including applicable privacy laws.

The protocol, protocol amendments, ICD, SRSD(s), and other relevant documents (eg, advertisements) must be reviewed and approved by the sponsor and submitted to an IRB/EC by the investigator and reviewed and approved by the IRB/EC before the study is initiated.

Any amendments to the protocol will require IRB/EC approval before implementation of changes made to the study design, except for changes necessary to eliminate an immediate hazard to study participants.

The investigator will be responsible for the following:

- Providing written summaries of the status of the study to the IRB/EC annually or more frequently in accordance with the requirements, policies, and procedures established by the IRB/EC;
- Notifying the IRB/EC of SAEs or other significant safety findings as required by IRB/EC procedures;
- Providing oversight of the conduct of the study at the site and adherence to requirements of 21 CFR, ICH guidelines, the IRB/EC, European regulation 536/2014 for clinical studies (if applicable), and all other applicable local regulations.

10.1.1.1. Reporting of Safety Issues and Serious Breaches of the Protocol or ICH GCP

In the event of any prohibition or restriction imposed (ie, clinical hold) by an applicable regulatory authority in any area of the world, or if the investigator is aware of any new information that might influence the evaluation of the benefits and risks of the study intervention, Pfizer should be informed immediately.

In addition, the investigator will inform Pfizer immediately of any urgent safety measures taken by the investigator to protect the study participants against any immediate hazard, and of any serious breaches of this protocol or of ICH GCP that the investigator becomes aware of.

10.1.2. Financial Disclosure

Investigators and sub investigators will provide the sponsor with sufficient, accurate financial information as requested to allow the sponsor to submit complete and accurate financial certification or disclosure statements to the appropriate regulatory authorities. Investigators are responsible for providing information on financial interests during the course of the study and for 1 year after completion of the study.

10.1.3. Informed Consent Process

The investigator or his/her representative will explain the nature of the study to the participant or his/her legally authorized representative and answer all questions regarding the study. The participant or his/her legally authorized representative should be given sufficient time and opportunity to ask questions and to decide whether or not to participate in the trial.

Participants must be informed that their participation is voluntary. Participants or their legally authorized representative will be required to sign a statement of informed consent that meets the requirements of 21 CFR 50, local regulations, ICH guidelines, HIPAA requirements, where applicable, and the IRB/EC or study center.

The investigator must ensure that each study participant or his or her legally authorized representative is fully informed about the nature and objectives of the study, the sharing of data related to the study, and possible risks associated with participation, including the risks associated with the processing of the participant's personal data.

The participant must be informed that his/her personal study-related data will be used by the sponsor in accordance with local data protection law. The level of disclosure must also be explained to the participant.

The participant must be informed that his/her medical records may be examined by Clinical Quality Assurance auditors or other authorized personnel appointed by the sponsor, by appropriate IRB/EC members, and by inspectors from regulatory authorities.

The investigator further must ensure that each study participant or his or her legally authorized representative is fully informed about his or her right to access and correct his or her personal data and to withdraw consent for the processing of his or her personal data.

The medical record must include a statement that written informed consent was obtained before the participant was enrolled in the study and the date the written consent was obtained. The authorized person obtaining the informed consent must also sign the ICD.

Participants must be reconsented to the most current version of the ICD(s) during their participation in the study.

A copy of the ICD(s) must be provided to the participant or the participant's legally authorized representative.

10.1.4. Data Protection

All parties will comply with all applicable laws, including laws regarding the implementation of organizational and technical measures to ensure protection of participant data.

Participants' personal data will be stored at the study site in encrypted electronic and/or paper form and will be password protected or secured in a locked room to ensure that only authorized study staff have access. The study site will implement appropriate technical and organizational measures to ensure that the personal data can be recovered in the event of disaster. In the event of a potential personal data breach, the study site will be responsible for determining whether a personal data breach has in fact occurred and, if so, providing breach notifications as required by law.

To protect the rights and freedoms of participants with regard to the processing of personal data, participants will be assigned a single, participant-specific numerical code. Any participant records or data sets that are transferred to the sponsor will contain the numerical code; participant names will not be transferred. All other identifiable data transferred to the sponsor will be identified by this single, participant-specific code. The study site will maintain a confidential list of participants who participated in the study, linking each participant's numerical code to his or her actual identity and medical record identification. In case of data transfer, the sponsor will protect the confidentiality of participants' personal data consistent with the clinical study agreement and applicable privacy laws.

10.1.5. Dissemination of Clinical Study Data

Pfizer fulfills its commitment to publicly disclose clinical study results through posting the results of studies on www.clinicaltrials.gov (ClinicalTrials.gov), the EudraCT, and/or www.pfizer.com, and other public registries in accordance with applicable local laws/regulations. In addition, Pfizer reports study results outside of the requirements of local laws/regulations pursuant to its SOPs.

In all cases, study results are reported by Pfizer in an objective, accurate, balanced, and complete manner and are reported regardless of the outcome of the study or the country in which the study was conducted.

www.clinicaltrials.gov

Pfizer posts clinical trial results on www.clinicaltrials.gov for Pfizer-sponsored interventional studies (conducted in patients) that evaluate the safety and/or efficacy of a product, regardless of the geographical location in which the study is conducted. These results are submitted for posting in accordance with the format and timelines set forth by US law.

EudraCT

Pfizer posts clinical trial results on EudraCT for Pfizer-sponsored interventional studies in accordance with the format and timelines set forth by EU requirements.

[www\(pfizer.com](http://www(pfizer.com)

Pfizer posts public disclosure synopses (CSR synopses in which any data that could be used to identify individual participants have been removed) on [www\(pfizer.com](http://www(pfizer.com) for Pfizer-sponsored interventional studies at the same time the corresponding study results are posted to www.clinicaltrials.gov.

Documents within marketing authorization packages/submissions

Pfizer complies with the European Union Policy 0070, the proactive publication of clinical data to the EMA website. Clinical data, under Phase 1 of this policy, includes clinical overviews, clinical summaries, CSRs, and appendices containing the protocol and protocol amendments, sample CRFs, and statistical methods. Clinical data, under Phase 2 of this policy, includes the publishing of individual participant data. Policy 0070 applies to new marketing authorization applications submitted via the centralized procedure since 01 January 2015 and applications for line extensions and for new indications submitted via the centralized procedure since 01 July 2015.

Data Sharing

Pfizer provides researchers secure access to patient-level data or full CSRs for the purposes of “bona-fide scientific research” that contributes to the scientific understanding of the disease, target, or compound class. Pfizer will make available data from these trials 24 months after study completion. Patient-level data will be anonymized in accordance with applicable privacy laws and regulations. CSRs will have personally identifiable information redacted.

Data requests are considered from qualified researchers with the appropriate competencies to perform the proposed analyses. Research teams must include a biostatistician. Data will not be provided to applicants with significant conflicts of interest, including individuals requesting access for commercial/competitive or legal purposes.

10.1.6. Data Quality Assurance

All participant data relating to the study will be recorded on printed or electronic CRF unless transmitted to the sponsor or designee electronically (eg, laboratory data). The investigator is responsible for verifying that data entries are accurate and correct by physically or electronically signing the CRF.

The investigator must maintain accurate documentation (source data) that supports the information entered in the CRF.

The investigator must ensure that the CRFs are securely stored at the study site in encrypted electronic and/or paper form and are password protected or secured in a locked room to prevent access by unauthorized third parties.

The investigator must permit study-related monitoring, audits, IRB/EC review, and regulatory agency inspections and provide direct access to source data documents. This verification may also occur after study completion. It is important that the investigator(s) and

PFIZER CONFIDENTIAL

their relevant personnel are available during the monitoring visits and possible audits or inspections and that sufficient time is devoted to the process.

Monitoring details describing strategy (eg, risk-based initiatives in operations and quality such as risk management and mitigation strategies and analytical risk-based monitoring), methods, responsibilities, and requirements, including handling of noncompliance issues and monitoring techniques (central, remote, or on-site monitoring), are provided in the monitoring plan.

The sponsor or designee is responsible for the data management of this study, including quality checking of the data.

Study monitors will perform ongoing source data verification to confirm that data entered into the CRF by authorized site personnel are accurate, complete, and verifiable from source documents; that the safety and rights of participants are being protected; and that the study is being conducted in accordance with the currently approved protocol and any other study agreements, ICH GCP, and all applicable regulatory requirements.

Records and documents, including signed ICDs, pertaining to the conduct of this study must be retained by the investigator for 15 years after study completion unless local regulations or institutional policies require a longer retention period. No records may be destroyed during the retention period without the written approval of the sponsor. No records may be transferred to another location or party without written notification to the sponsor. The investigator must ensure that the records continue to be stored securely for as long as they are maintained.

When participant data are to be deleted, the investigator will ensure that all copies of such data are promptly and irrevocably deleted from all systems.

The investigator(s) will notify the sponsor or its agents immediately of any regulatory inspection notification in relation to the study. Furthermore, the investigator will cooperate with the sponsor or its agents to prepare the investigator site for the inspection and will allow the sponsor or its agent, whenever feasible, to be present during the inspection. The investigator site and investigator will promptly resolve any discrepancies that are identified between the study data and the participant's medical records. The investigator will promptly provide copies of the inspection findings to the sponsor or its agent. Before response submission to the regulatory authorities, the investigator will provide the sponsor or its agents with an opportunity to review and comment on responses to any such findings.

10.1.7. Source Documents

Source documents provide evidence for the existence of the participant and substantiate the integrity of the data collected. Source documents are filed at the investigator site.

Data reported on the CRF or entered in the eCRF that are from source documents must be consistent with the source documents or the discrepancies must be explained. The

investigator may need to request previous medical records or transfer records, depending on the study. Also, current medical records must be available.

Definition of what constitutes source data can be found in the clinical monitoring plan.

Description of the use of computerized system is documented in the Data Management Plan.

10.1.8. Study and Site Start and Closure

The study start date is the date on which the clinical study will be open for recruitment of participants.

The first act of recruitment is the date of the first participant's first visit and will be the study start date.

The sponsor designee reserves the right to close the study site or terminate the study at any time for any reason at the sole discretion of the sponsor. Study sites will be closed upon study completion. A study site is considered closed when all required documents and study supplies have been collected and a study-site closure visit has been performed.

The investigator may initiate study-site closure at any time upon notification to the sponsor if requested to do so by the responsible IRB/EC or if such termination is required to protect the health of study participants.

Reasons for the early closure of a study site by the sponsor may include but are not limited to:

- Failure of the investigator to comply with the protocol, the requirements of the IRB/EC or local health authorities, the sponsor's procedures, or GCP guidelines;
- Discontinuation of further study intervention development.

If the study is prematurely terminated or suspended, the sponsor shall promptly inform the investigators, the ECs/IRBs, the regulatory authorities, and any CRO(s) used in the study of the reason for termination or suspension, as specified by the applicable regulatory requirements. The investigator shall promptly inform the participant and should assure appropriate participant therapy and/or follow-up.

Study termination is also provided for in the clinical study agreement. If there is any conflict between the contract and this protocol, the contract will control as to termination rights.

10.1.9. Publication Policy

The results of this study may be published or presented at scientific meetings by the investigator after publication of the overall study results or 1 year after the end of the study (or study termination), whichever comes first.

The investigator agrees to refer to the primary publication in any subsequent publications such as secondary manuscripts, and submits all manuscripts or abstracts to the sponsor 30 days before submission. This allows the sponsor to protect proprietary information and to

PFIZER CONFIDENTIAL

provide comments and the investigator will, on request, remove any previously undisclosed confidential information before disclosure, except for any study- or Pfizer intervention-related information necessary for the appropriate scientific presentation or understanding of the study results.

For all publications relating to the study, the investigator will comply with recognized ethical standards concerning publications and authorship, including those established by the International Committee of Medical Journal Editors.

The sponsor will comply with the requirements for publication of the overall study results covering all investigator sites. In accordance with standard editorial and ethical practice, the sponsor will support publication of multicenter studies only in their entirety and not as individual site data. In this case, a coordinating investigator will be designated by mutual agreement.

Authorship of publications for the overall study results will be determined by mutual agreement and in line with International Committee of Medical Journal Editors authorship requirements.

If publication is addressed in the clinical study agreement, the publication policy set out in this section will not apply.

10.1.10. Sponsor's Qualified Medical Personnel

The contact information for the sponsor's appropriately qualified medical personnel for the study is documented in the study contact list located in the supporting study documentation.

To facilitate access to appropriately qualified medical personnel on study-related medical questions or problems, participants are provided with a contact card at the time of informed consent. The contact card contains, at a minimum, protocol and study intervention identifiers, participant numbers, contact information for the investigator site, and contact details for a contact center in the event that the investigator site staff cannot be reached to provide advice on a medical question or problem originating from another healthcare professional not involved in the participant's participation in the study. The contact number can also be used by investigator staff if they are seeking advice on medical questions or problems; however, it should be used only in the event that the established communication pathways between the investigator site and the study team are not available. It is therefore intended to augment, but not replace, the established communication pathways between the investigator site and the study team for advice on medical questions or problems that may arise during the study. The contact number is not intended for use by the participant directly, and if a participant calls that number, he or she will be directed back to the investigator site.

10.2. Appendix 2: Clinical Laboratory Tests

Clinical laboratory tests will be conducted as per standard of care at the individual Study site. They will not be collected in the CRF. The laboratory tests described in the table below are recommended to determine participant dosing eligibility. Unscheduled clinical laboratory measurements may be obtained at any time during the study to assess any perceived safety issues. As per the investigator's evaluation, if any laboratory test is determined as an AE or SAE, this should be reported to the Sponsor as described in [Appendix 3](#).

Hematology	Blood Chemistry	Urinalysis (microscopic analysis ^a)	Coagulation Tests
Hemoglobin	ALT	If urine dipstick is positive for protein, perform U/A with microscopy. If U/A with microscopy shows $\geq 2+$ protein, collect 24-hour urine for protein.	aPTT
Platelets	AST	Urine dipstick positive for urine blood: Collect a U/A with microscopy (unless dipstick hematuria can be explained by local bleeding such as menses).	INR
WBC	Alk Phos	Specific Gravity	
Neutrophils	Sodium	pH	
Lymphocytes	Potassium	Protein	
Monocytes	Magnesium	Glucose	
Eosinophils	Chloride	RBC	
Basophils	Calcium	WBC	
Blast Count	Total Bilirubin	Ketones	
	BUN or Urea	Leukocyte Esterase	
	Creatinine	Nitrite	
	Uric Acid		
	Glucose (non-fasting)		
	Albumin		
	Total Protein		
	Phosphorus		
	LDH		
	CPK		
	Bicarbonate		

a. Only if urine dipstick is positive for blood, protein, nitrites, or leukocyte esterase. If the dipstick is positive for blood, protein, nitrites and leukocytes, suggestive of UTI, then send sample for laboratory microscopy and culture.

Investigators must document their review of each laboratory safety report.

10.3. Appendix 3: Adverse Events: Definitions and Procedures for Recording, Evaluating, Follow-up, and Reporting

10.3.1. Definition of AE

AE Definition

• An AE is any untoward medical occurrence in a patient or clinical study participant, temporally associated with the use of study intervention, whether or not considered related to the study intervention.• NOTE: An AE can therefore be any unfavorable and unintended sign (including an abnormal laboratory finding), symptom, or disease (new or exacerbated) temporally associated with the use of study intervention.

Events Meeting the AE Definition

• Any abnormal laboratory test results (hematology, clinical chemistry, or urinalysis) or other safety assessments (eg, ECG, radiological scans, vital sign measurements), including those that worsen from baseline, considered clinically significant in the medical and scientific judgment of the investigator. Any abnormal laboratory test results that meet any of the conditions below must be recorded as an AE:
• Is associated with accompanying symptoms.• Requires additional diagnostic testing or medical/surgical intervention.• Leads to a change in study dosing (outside of any protocol-specified dose adjustments) or discontinuation from the study, significant additional concomitant drug treatment, or other therapy.• Exacerbation of a chronic or intermittent preexisting condition including either an increase in frequency and/or intensity of the condition.• New conditions detected or diagnosed after study intervention administration even though it may have been present before the start of the study.• Signs, symptoms, or the clinical sequelae of a suspected drug-drug interaction.• Signs, symptoms, or the clinical sequelae of a suspected overdose of either study intervention or a concomitant medication. Overdose per se will not be reported as an AE/SAE unless it is an intentional overdose taken with possible suicidal/self-harming intent. Such overdoses should be reported regardless of sequelae.• The signs, symptoms, and/or clinical sequelae resulting from lack of efficacy will be reported as an AE or SAE if they fulfill the definition of an AE or SAE and meet the requirements as per Section 8.3.8.1. Also, “lack of efficacy” or “failure of expected pharmacological action” does not constitute an AE or SAE.

Events NOT Meeting the AE Definition

- Any clinically significant abnormal laboratory findings or other abnormal safety assessments which are associated with the underlying disease, unless judged by the investigator to be more severe than expected for the participant's condition.
- The disease/disorder being studied or expected progression, signs, or symptoms of the disease/disorder being studied, unless more severe than expected for the participant's condition.
- Medical or surgical procedure (eg, endoscopy, appendectomy): the condition that leads to the procedure is the AE.
- Situations in which an untoward medical occurrence did not occur (social and/or convenience admission to a hospital).
- Anticipated day-to-day fluctuations of preexisting disease(s) or condition(s) present or detected at the start of the study that do not worsen.
- Worsening of signs and symptoms of the malignancy under study should be recorded as AEs in the appropriate section of the CRF. Disease progression assessed by measurement of malignant lesions on radiographs or other methods should not be reported as AEs.

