8.3.1.2. Recording Nonserious AEs and SAEs on the CRF

All nonserious AEs and SAEs occurring in a participant during the active collection period, which begins after obtaining informed consent as described in [Section 8.3.1](#), will be recorded on the AE section of the CRF.

The investigator is to record on the CRF all directly observed and all spontaneously reported AEs and SAEs reported by the participant.

If a participant begins a new anticancer therapy, the recording period for nonserious AEs ends at the time the new treatment is started; however, SAEs must continue to be recorded on the CRF during the above-indicated active collection period. Note that a switch to a commercially available version of the study intervention is considered as a new anticancer therapy for the purposes of SAE reporting.

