8.3.8.1. Lack of Efficacy

Lack of efficacy is reportable to Pfizer Safety **only** if associated with an SAE. Refer to [Appendix 3, Section 10.3.1](#) for additional information.

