- Examples of such events include invasive or malignant cancers, intensive treatment in an emergency room or at home for allergic bronchospasm, blood dyscrasias or convulsions that do not result in hospitalization, or development of drug dependency or drug abuse.

- Progression of the malignancy under study (including signs and symptoms of progression) should not be reported as an SAE unless the outcome is fatal within the active collection period. Hospitalization due to signs and symptoms of disease progression should not be reported as an SAE. If the malignancy has a fatal outcome during the study or within the active collection period, then the event leading to death must be recorded as an AE on the CRF, and as an SAE with CTCAE Grade 5 (see the Assessment of Intensity section).
- If the HIV-related disease has a fatal outcome during the study or within the active collection period, then the event leading to death must be recorded as an AE on the CRF and as an SAE.
- Suspected transmission via a Pfizer product of an infectious agent, pathogenic or non-pathogenic, is considered serious. The event may be suspected from clinical symptoms or laboratory findings indicating an infection in a patient exposed to a Pfizer product. The terms “suspected transmission” and “transmission” are considered synonymous. These cases are considered unexpected and handled as serious expedited cases by pharmacovigilance personnel. Such cases are also considered for reporting as product defects, if appropriate.

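### Appendix 3 gives conflicting rules on whether nonfatal signs and symptoms of worsening disease enter the AE data, the study's only endpoint

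*Protocol*

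**What the plan says.** The only endpoint under Amendment 6 is the full set of AEs and SAEs (Protocol Section 3; SAP Section 2.1). Protocol Section 8.3 refers the reader to Appendix 3 for what counts as either. Section 8.3.1.2 then sends "All nonserious AEs and SAEs occurring in a participant during the active collection period" to the AE section of the CRF.

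Four places in Appendix 3 bear on worsening disease:

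- **Section 10.3.1, events that meet the AE definition.** Signs, symptoms and sequelae of lack of efficacy are reported as an AE or SAE "if they fulfill the definition of an AE or SAE and meet the requirements as per Section 8.3.8.1". Section 8.3.8.1 holds one rule, "Lack of efficacy is reportable to Pfizer Safety only if associated with an SAE", and then points back to Section 10.3.1.
- **Section 10.3.1, events that do not meet the AE definition, second bullet.** This excludes the disease under study and its "expected progression, signs, or symptoms of the disease/disorder being studied, unless more severe than expected".
- **The same list, last bullet.** "Worsening of signs and symptoms of the malignancy under study should be recorded as AEs in the appropriate section of the CRF". Only progression measured on imaging or by other methods is kept out.
- **Section 10.3.2.** "Progression of the malignancy under study (including signs and symptoms of progression) should not be reported as an SAE unless the outcome is fatal", with the fatal outcome falling in the active collection period. "Hospitalization due to signs and symptoms of disease progression should not be reported as an SAE". A fatal malignancy outcome must be recorded as an AE and as a Grade 5 SAE. The opening paragraph of the same section, however, names death from progression as an example of an event that cannot be an SAE.

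**The concern.** A threshold for expedited reporting to the sponsor's safety group has been written into the definition of what is an AE. A few lines later, an instruction to record much the same events appears in the list of events that are not AEs. A site that follows the first text can leave out a nonserious symptom of worsening disease. A site that follows the second will enter it.

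This matters more here than in most trials. Efficacy assessments are not applicable (Protocol Section 8.1). Disease assessments and laboratory tests stay in the medical record unless a finding is called an AE (Section 8.2.4; Appendix 2). The SAP sets its sections on deaths, laboratory data and hospitalization to not applicable (Sections 6.3.2, 6.3.3 and 6.3.8). Reasons for discontinuation are summarized (SAP Section 6.2.2.1), but a symptom that is not entered as an AE appears in no other planned summary. Investigators assess causality for recorded AEs (Protocol Section 10.3.3), so an omitted event has no such assessment in the database.

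The situation is foreseeable, because treatment continues until progression, relapse, death, unacceptable toxicity or refusal (Protocol Section 6.1.3).

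**Working it through.** The plan gives no figure to reproduce, so the check sets the rules side by side and applies each to the same event.

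| Event | Lack-of-efficacy bullet, 10.3.1 (literal) | Expected-disease bullet, 10.3.1 | Worsening bullet, 10.3.1 | 10.3.2 |
|---|---|---|---|---|
| Nonserious worsening symptom, no associated SAE | Not an AE: 8.3.8.1 not met | Not an AE if expected | Record as AE | Not an SAE |
| Nonserious worsening symptom, associated with an SAE | AE | Not an AE if expected | Record as AE | Not an SAE |
| Nonfatal symptom of progression leading to hospitalization | Cannot meet 8.3.8.1 through its own seriousness | AE only if worse than expected | Record as AE | Meets SAE criterion c, but barred as an SAE by two sentences |
| Fatal progression | Not decisive | Not an AE if expected | Symptoms: AE | Opening paragraph: cannot be an SAE. Later bullet: AE and Grade 5 SAE |

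Step by step:

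1. **Does AE status depend on Section 8.3.8.1?** Yes, on a literal reading. The two conditions in Section 10.3.1 are joined by *and*. The only requirement in Section 8.3.8.1 is association with an SAE, and it is expressly a rule for reports to Pfizer Safety.
2. **Are nonfatal events barred from being SAEs?** Yes, for signs and symptoms of progression of the malignancy. The documents do not say this of every consequence of lack of efficacy.
3. **Is there still a route onto the CRF?** Yes. The last bullet of the exclusion list instructs sites to record worsening signs and symptoms as AEs.
4. **Do Section 8.3.1.2 and the table in Section 10.3.3 settle the matter?** No. They require every nonserious AE on the CRF and none on the SAE form, which confirms that recording and reporting are separate channels. But they presuppose that the event is an AE, and Section 8.3 leaves that question to Appendix 3.
5. **Do the two bullets in the exclusion list fit together?** Only in part. Expected, stable symptoms against worsening symptoms is a workable division. But the second bullet also excludes expected progression, which is itself worsening, so the two overlap.
6. **Does the hospitalization sentence carry the severity exception in Section 10.3.1?** No. An event can be an AE because it is worse than expected, meet the hospitalization criterion, and still be barred as an SAE.

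For scale only: at most 34 + 3 = 37 participants can continue, and the two source studies are summarized separately. One participant is 1/34 = 2.9% of the B1371019 group overall and 1/3 = 33.3% of the B1371012 group. The arm split is not given; an even split of 17 (an assumption) would make it 1/17 = 5.9% of an arm. The table of nonserious events in more than 5% of an arm (SAP Section 6.3.1.1) is entered by one participant in an arm of 19 (1/19 = 5.3%) but not of 20 (1/20 = 5.0%). These figures hold for any single event in a small group and do not measure this defect.

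**The case against.** The strongest reply is that the protocol does tell sites what to do. The worsening bullet is explicit and specific, Section 8.3.1.2 requires all AEs on the CRF, and the Section 10.3.3 table separates CRF recording from reports to Pfizer Safety. On this view Section 8.3.8.1 was never meant to control the CRF, and a sensible site would record. Section 8.3.8.1 also asks only for association with an SAE, so the symptom need not itself be serious.

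Much of this stands, and it rules out three stronger readings that a reader might infer:

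- **That nonfatal signs and symptoms cannot be recorded at all.** They can, under the worsening bullet.
- **That lack of efficacy and progression are the same thing.** The overlap is plausible in leukemia, but no section equates them. The bar in Section 10.3.2 applies only to signs of progression.
- **That a drug effect taken for loss of efficacy drops out of every table without a causality assessment.** Section 10.3.1 defines an AE regardless of relatedness. Section 10.3.3 requires causality for every AE, with the underlying disease weighed as an alternative cause. An event is lost only if a site follows the excluding text and disregards the worsening bullet.

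The reply does not remove the contradiction. The instruction it relies on is filed among events that are not AEs, and the bullet in the list of qualifying events says something different.

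**Conclusion.** The concern holds as a conflict between rules. Section 10.3.1 contains a misplaced condition and a misplaced instruction that give opposite answers for a nonserious symptom of worsening disease with no associated SAE. Section 10.3.2 adds a conflict on fatal progression and a hospitalization rule that lacks the exception given in Section 10.3.1. Because AEs and SAEs are the only endpoint, sites may differ in what reaches the treatment-emergent, serious and fatal AE tables.

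The size cannot be estimated. The documents give no expected number of such events and no indication of which text sites follow. The conclusion assumes that at least some sites would apply the cross-reference as worded, and, for the SAE part, that the signs in question are signs of progression. No analysis method is at fault; the definitions that feed the tables need correcting.

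**What to change.** Three wording changes in Appendix 3:

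1. In the lack-of-efficacy bullet of Section 10.3.1, delete the second condition (the reference to Section 8.3.8.1). State that Section 8.3.8.1 governs only reporting to Pfizer Safety.
2. Move the sentence on worsening signs and symptoms of the malignancy to the list of events that meet the AE definition. Keep the second bullet of the exclusion list for expected, non-worsening disease signs and symptoms, with a cross-reference to the moved sentence. Striking signs and symptoms from that bullet altogether would change what is collected, which goes further than reconciling the text.
3. In Section 10.3.2, reconcile the examples in the opening paragraph with both progression sentences (nonfatal signs and symptoms, and hospitalization) and with the fatal-outcome rule. State separately what is recorded on the CRF and what is reported as an SAE. Amending the hospitalization sentence alone would leave the preceding sentence and the examples in conflict.

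The cost is these edits and a few more AE entries in at most 37 participants.
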